#### 3. PARTICIPANT SELECTION

## 3.1 Eligibility Criteria

Participants must meet the following criteria on screening examination to be eligible to participate in the study:

- 3.1.1 Patients must have histologically determined classic Hodgkin lymphoma with pathologic review at the participating institution.
- 3.1.2 Participants must have measurable disease, defined as a lymph node or tumor mass ≥1.5 cm in at least one dimension by CT, PET/CT, or MR. Imaging must have been completed no greater than 6 weeks prior to study enrollment. Measurable disease that has previously been irradiated is permissible only if there has been evidence of progression since the radiation.
- 3.1.3 Patients must have progressed after two or more lines of systemic treatment, including autologous stem cell transplantation, if eligible.
- 3.1.4 Progression of disease or relapse following treatment with nivolumab or pembrolizumab. Intervening treatments with between PD-1 mAb therapy and the trial are permitted.
- 3.1.5 Patients may have had a prior autologous stem cell transplant and may have been treated with chimeric antigen receptor T-cells (CAR T-cells).
- 3.1.6 Age  $\geq$ 18 years.
- 3.1.7 Eastern Cooperative Oncology Group (ECOG) performance status 0-2 (see Appendix A)
- 3.1.8 Adequate hematologic and organ function as defined below:
  - Absolute neutrophil count >  $1.0 \times 10^9$ /L unless due to marrow involvement by lymphoma in which case ANC must be >0.75x10^9/L. Growth factor support is allowed provided it is received at least 5 days prior to enrollment labs.
  - Platelets > 75  $\times$  10^9/L, unless due to marrow involvement by lymphoma, in which case platelets must be >50  $\times$  10^9/L
  - Estimated GFR (by Cockroft-Gault equation) > 40ml/min
  - Total bilirubin < 1.5 X ULN
  - AST/ALT < 2.5 X ULN
- 3.1.9 Ability to understand and the willingness to sign a written informed consent document.

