- 3.1.10 Willingness to provide pre-treatment tumor sample by core needle or excisional surgical biopsy. An archival sample is acceptable in the following situations: the sample was acquired within 90 days of initiation of PD-1 therapy AND the following provisions are met: 1) availability of a tumor-containing formalin-fixed, paraffin-embedded (FFPE) tissue block, 2) if the tumor containing FFPE tissue block cannot be provided in total, sections from this block should be provided that are freshly cut and mounted on positively-charged glass slides (SuperFrost Plus are recommended). Preferably, 25 slides should be provided; if not possible, a minimum of 15 slides is required. Exceptions to this criterion may be made with approval of the Study Chair.

DF/HCC Protocol #: 21-204 Protocol version date: v8/06 September 2023

3.1.11 Willingness to use contraception during and after study treatment. Women of child-baring potential (WOCBP) will be instructed to adhere to contraception for a period of 5 months following last dose of nivolumab and 6 months following the last dose of ipilimumab. Men receiving nivolumab and who are sexually active with WOCBP will be instructed to adhere to contraception for a period of 7 months after last dose of nivolumab and 6 months after the last dose of ipilimumab.

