Tumor biopsies (pre-treatment, on-treatment, and post-progression) and serial peripheral blood samples will be used to identify possible genetic or immune biomarkers of response. When safely feasible, tumor biopsy (excisional or core needle) will be obtained at baseline (unless an archival sample within 90 days and without intervening treatment is available with at least 15 unstained slides). In addition, patients will undergo an optional core needle biopsy between day 14 and 21 of cycle 1 of therapy. When feasible, a core needle biopsy will also be obtained at the time of progression. Serial peripheral blood will be collected for research purposes (see Section 9).

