# 9. BIOMARKER, CORRELATIVE, AND SPECIAL STUDIES

The biomarkers for the trial include measurements from tumor tissues and analyses of blood samples to explore molecular, cellular, and soluble markers that may be relevant to the mechanism of action of the drug(s) or response/resistance to the drug(s). The correlative studies are best described as ancillary. While the goal of the correlative studies is to provide supportive data for the clinical study, there may be circumstances when a decision is made to stop a collection, not perform, or discontinue an analysis due to practical reasons (e.g., inadequate sample number), issues related to the quality of the sample, or issues related to the assay that preclude analysis, etc). Therefore, depending on the results obtained during the study, sample collection/analysis may be omitted at the discretion of the PI.

A cheek swab/saliva sample will be collected prior to treatment. In addition, peripheral blood will be collected for research at baseline, and after 3, 6, 12, 24, and 48 weeks of therapy. In

addition, peripheral blood samples will be collected at the time of progression (when feasible). Analyses of these samples may include investigation of ctDNA, such as quantification of ctDNA at different timepoints and examination of changes in copy number abnormalities and relevant pathogenic genes.

When safely feasible, tumor biopsies (excisional or core needle) will be obtained at baseline, between day 14 and 21 of cycle 1 of therapy (optional), and at the time of progression (optional). An archival sample within 90 days and without intervening treatment is acceptable as the pretreatment biopsy assuming that the following provisions are met: 1) Priority: tumor containing formalin-fixed, paraffin-embedded (FFPE) tissue block; 2) Priority: if the tumor containing FFPE tissue block cannot be provided in total, sections from this block should be provided that are freshly cut and mounted on positively-charged glass slides (SuperFrost Plus are recommended). Preferably, 25 slides should be provided; if not possible, a minimum of 15 slides is required.

These may be obtained by excisional or core needle biopsy. Biopsies may be analyzed for tumor and microenvironmental expression of checkpoint markers and for immune architecture by a combination of immunohistochemistry and multiparameter spectral imaging. Ideally, 5-6 core needle biopsies will be collected.

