# 10.1 Required Data for Study Screening

The following must be obtained within 28 days prior to the 1st day of treatment:

- Medical history, medication review, physical exam, vital signs, height and weight, ECOG performance status (see Appendix A)
- CBC with manual differential, blood chemistries including complete metabolic panel, phosphorus, magnesium, uric acid, LDH, TSH, creatinine kinase, lipase, triglycerides, PT/INR, PTT, hepatitis C antibody, hepatitis B surface antigen and hepatitis B core antibody. Urine studies to include a urine dipstick for blood and protein and if positive (2+ or greater for protein) a microscopic urinalysis and 24-hour urine collection (for protein).
- Serum or urine β-HCG for females of childbearing potential
- Tumor restaging (within 6 weeks). This will consist of PET/CT scans (including neck, chest, abdomen/pelvis).
- Peripheral blood sample for biomarker studies (Section 9).
- Tumor biopsy for biomarker studies (Section 9). An archival sample may be acceptable (see Section 3.1).
- 12-Lead Electrocardiogram (EKG).

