- k: All patients are required to provide a pre-treatment core needle or excisional biopsy or an archival sample provided it was obtained within 90 days of trial initiation (see section 3.1). In addition, optional core needle biopsies may be collected during cycle 1 (between day 14-21) and at the time of progression.
- l: PET/CT scans will be performed at baseline and after 4 doses of ipilimumab monotherapy (week 12). Among ipilimumab responders, restaging scans will occur prior to ipilimumab maintenance cycle 2 (week 24), cycle 3 (week 36), cycle 5 (week 60), and cycle 7 (week 84). Among ipilimumab non-responders, restaging scans will occur after 4 cycles of ipilimumab + nivolumab combination therapy (week 24) and prior to ipilimumab maintenance cycle 2 (week 36), cycle 4 (week 60), and cycle 6 (week 84).. The end-of-treatment assessment will occur 4-12 weeks after the last doses of study therapy (i.e. weeks 112-120 for patients who complete all planned study therapy). Afterwards patients will be re-imaged every 24 weeks.

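### Criterion 3.1.10 counts the archival-tissue window from the start of PD-1 therapy and sets no bar on later treatment, in conflict with Sections 5 and 9 and Table 7 footnote k; only the exploratory tissue analyses and eligibility checks are affected

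*Combined protocol and SAP*

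**What the plan says.** Four places set a time window for archival tissue.

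- **Section 3.1.10 (eligibility):** archival tissue is acceptable if "the sample was acquired within 90 days of initiation of PD-1 therapy", subject to block or slide requirements. Nothing is said about treatment after the biopsy. The Study Chair may approve exceptions.
- **Section 5 (text under the trial schema):** a baseline biopsy is taken when safe "unless an archival sample within 90 days and without intervening treatment is available with at least 15 unstained slides".
- **Section 9 (biomarkers):** "An archival sample within 90 days and without intervening treatment is acceptable as the pretreatment biopsy", with the same slide provisions.
- **Table 7 footnote k (study calendar):** a fresh biopsy, or an "archival sample provided it was obtained within 90 days of trial initiation", with a pointer to Section 3.1.

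Section 10.1 sets no window and also points to Section 3.1. On prior therapy, 3.1.4 requires "Progression of disease or relapse following treatment with nivolumab or pembrolizumab" and adds that "Intervening treatments with between PD-1 mAb therapy and the trial are permitted".

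**The concern.** PD-1 failure is an entry condition, so the PD-1 therapy in 3.1.10 is most naturally the patient's earlier course. That start date may lie well before the trial, with the PD-1 course itself and possibly other lines in between. The other three places are plainly after a recent specimen.

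What is at stake is the meaning of baseline in the correlative work. Section 2.5.1 hypothesises that baseline microenvironment features predict response to study treatment, and plans to describe changes using on-treatment and post-progression samples. If some baseline specimens predate PD-1 exposure, an apparent change on study treatment cannot be told apart from an effect of the earlier PD-1 antibody or of a later line. Mixing such specimens with recent ones adds a source of variation that 13 patients cannot resolve.

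There is also a practical problem: a site following 3.1.10 and a site following Section 9 could reach opposite decisions on the same block.

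**Working it through.** The point rests on text, so the rules are set side by side.

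| Place | 90 days counted from | Treatment since biopsy | Points to 3.1? |
|---|---|---|---|
| 3.1.10 | start of PD-1 therapy | no condition | n/a |
| Section 5 | not stated; context implies baseline | barred | no |
| Section 9 | not stated; context implies pre-treatment | barred | no |
| Footnote k | trial initiation | no condition | yes |

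No two of 3.1.10, the Section 5 and 9 pair, and footnote k give the same rule, and none of the four places states both a trial-based reference date and a treatment bar.

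**Could 3.1.10 mean on-trial nivolumab?** No. Under Sections 5 and 5.1 nivolumab is given only after ipilimumab monotherapy, to clinically stable patients with stable or progressive disease. Its start date is unknown at registration, and some patients will never receive it.

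**Which text governs?** Section 4.1 has an investigator confirm the eligibility criteria and the study team complete an eligibility checklist before registration. Section 10.1 and footnote k both send the reader to Section 3.1. The rule applied in practice is therefore 3.1.10.

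**Can one archival sample satisfy both 3.1.10 and Sections 5 and 9?** Let day 0 be the first protocol dose, B the biopsy day and P the day prior PD-1 therapy began. Take day 0 as the implied reference date in Sections 5 and 9 (an assumption).

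1. Sections 5 and 9: B is no earlier than day −90, with no treatment between B and day 0.
2. 3.1.10: B and P are at most 90 days apart. The text does not say before or after.
3. If B precedes P, the PD-1 course itself falls between biopsy and trial, so Sections 5 and 9 are failed in every case.
4. If B follows P, the PD-1 course and any later line must be over by B, and B is at most 90 days after P. Both rules are met only if all treatment from the PD-1 start onward finished within 90 days, which also puts P no earlier than day −180 (90 + 90).

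The overlap exists but is narrow. As a rough guide, Section 2.3.4 reports a median of 21 nivolumab doses every 2 weeks in the pooled studies; 20 intervals × 14 days = 280 days from first to last dose. Those patients were not selected for PD-1 failure as these are, so this indicates scale only. Section 2.4 puts rapid progression on PD-1 blockade at about 10–15%.

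**Two examples.**

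- Tissue taken just before a PD-1 course that began a year ago meets 3.1.10. It fails Sections 5 and 9 (the PD-1 course intervened) and fails footnote k (more than 90 days old).
- Tissue taken 60 days before the first protocol dose, with no treatment since, meets Sections 5 and 9 and footnote k. It fails 3.1.10 if PD-1 therapy began more than 90 days before that biopsy.

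**Does the primary test depend on this?** Section 13.3 rejects a 10% response rate if at least 4 of 13 respond. From the exact binomial:

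- type 1 error = 1 − (0.2542 + 0.3672 + 0.2448 + 0.0997) = 0.034
- power at 40% = 1 − (0.0013 + 0.0113 + 0.0453 + 0.1107) = 0.831

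Both match the stated 0.034 and 0.83. Tissue age enters neither.

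**The case against.** The strongest case on the other side is that little hangs on this. Section 13.4 says the correlative work is unpowered, hypothesis-generating and dependent on samples and budget. Section 9 calls it ancillary and lets the principal investigator omit collection or analysis. A fresh biopsy satisfies all four places, and 3.1.10 asks for willingness to provide tissue, with Study Chair exceptions available. Section 2.4 also reports frequent CTLA-4 and CD86 expression both before and after PD-1 blockade, so older tissue may still inform on the target pathway.

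The limit on consequence stands. The rest only partly answers the point. Hypothesis-generating work still needs to know which disease state was sampled. Similar expression of two markers does not make specimens interchangeable when Section 9 also covers T-cell subsets, NK cells, macrophages and PD-1/PD-L1. The exception clause in 3.1.10 has no criteria, so it could widen the mix of samples, and it sits awkwardly with Appendix B 3.5.3, which requires IRB approval for eligibility exceptions.

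Three stronger readings are tempting and are not supported:

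- **That the other three places all require recent tissue with no treatment in between.** None states both a trial-based date and a treatment bar.
- **That tissue valid under Sections 5 and 9 always fails 3.1.10.** A patient with a short, recent PD-1 course could meet both.
- **That a definite share of baselines is from the wrong disease state.** One might suppose a quarter to a half of patients use archival tissue and arrive at 3 to 6 of 13. The documents give no archival-use rate, and 3.1.10 can also admit tissue taken after PD-1 therapy began, so not every archival sample would be unsuitable.

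**Conclusion.** The inconsistency is real, nothing elsewhere in the protocol resolves it, and the conflicting rule is the one applied at registration. It can err in both directions: admitting tissue that predates PD-1 exposure, and refusing recent tissue that Sections 5 and 9 accept.

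The number of patients affected is unknown, anywhere from 0 to 13; each would be 1 of 13 (7.7%) at full enrolment, or a larger share if fewer patients have usable baseline tissue. The conclusion assumes that PD-1 therapy in 3.1.10 means the patient's prior course and that the implied reference date in Sections 5 and 9 is the start of protocol treatment. A reader might infer a threat to the main efficacy conclusion; there is none, since the response-rate test, its error rate and its power do not use the tissue. This is worth correcting by amendment because the correction is cheap and the baseline specimen anchors the planned microenvironment comparisons.

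**What to change.** State one rule in identical words in 3.1.10, Section 5, Section 9 and Table 7 footnote k: archival tissue is acceptable if obtained in the 90 days before the patient's first dose of protocol therapy, with no anticancer treatment between biopsy and that dose. This supplies the missing reference date in Sections 5 and 9. It also replaces the trial-initiation wording in footnote k, which could mean the opening of the trial or the patient's own start.

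For samples already accepted under 3.1.10 or by Study Chair exception, record the biopsy date and all treatments since biopsy. Flag those taken before PD-1 therapy and, as a descriptive sensitivity check, repeat the baseline biomarker summaries without them. Formal subgroup comparison is not sensible at this sample size.

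The cost is a short amendment, a checklist update and two data items per sample. Somewhat fewer archival samples will qualify under 3.1.10, so some patients may need a fresh biopsy; Sections 5 and 9 already exclude samples with treatment in between.

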#### 3.2 Exclusion Criteria

- 3.2.1 Patients currently receiving anticancer therapies or who have received anticancer therapies within 28 days of the start of study drug (including chemotherapy, radiation therapy, antibody-based therapy, etc.), or 56 days for radioimmunotherapy. Steroids for symptom palliation are allowed but must be either discontinued or on stable doses of < 10mg daily of prednisone (or the equivalent) at the time of initiation of protocol therapy.
- 3.2.2 Patients may not be receiving any other investigational agents or have received investigational agents within 4 weeks (or 3 half-lives, whichever is longer) of beginning treatment.
- 3.2.3 History of severe allergic or anaphylactic reactions to monoclonal antibody therapy unless in consultation with an allergy specialist they are deemed eligible for retreatment with desensitization.
- 3.2.4 Patients who have undergone prior allogeneic stem cell transplantation
- 3.2.5 Patients with a history of or active autoimmune disease (except controlled asthma, Hashimoto thyroiditis, atopic dermatitis, or vitiligo), or requiring systemic corticosteroids at a dose of 10mg prednisone equivalent daily. Patients with a history of autoimmune disease who never required corticosteroids and with no evidence of disease activity, and in whom the risk of reactivation is felt not to be serious, may be enrolled after discussion with the overall study chair. Exceptions to this are patients with a history of inflammatory bowel disease (ulcerative colitis and Crohn's disease). These patients are excluded regardless of whether their disease is active or inactive.
- 3.2.6 Patients who experienced grade 4 immune-related adverse events (irAEs) during treatment with a PD-1 mAb.
- 3.2.7 Patients with active pneumonitis or colitis, or patients with cirrhosis.
- 3.2.8 Patients, who have had a major surgery or significant traumatic injury within 4 weeks of start of study drug, patients who have not recovered from the side effects of any major surgery (defined as requiring general anesthesia).
- 3.2.9 Patients with known HIV infection or hepatitis B or C infection. Testing for HIV is optional. Testing for hepatitis B and C is mandatory. Patients with hepatitis B core Ab positivity but negative surface antigen and negative viral load may be enrolled if they can be treated with a prophylactic agent (eg, entecavir); patients with hepatitis C seropositivity who have a negative viral load can also be enrolled.
- 3.2.10 Patients with a systemic fungal, bacterial, viral, or other infection not controlled (defined as exhibiting ongoing signs/symptoms related to the infection and without improvement, despite appropriate antibiotics or other treatment).
- 3.2.11 Prior history of another malignancy (except for non-melanoma skin cancer or *in situ* cervical or breast cancer) unless disease free for at least 2 years. Patients with prostate cancer are allowed if PSA is less than 1.
- 3.2.12 Patients should not have received immunization with attenuated live vaccine within one week of study entry or during study period.
- 3.2.13 History of noncompliance to medical regimens.

Protocol version date: v8/06 September 2023

- 3.2.14 Patients who have any severe and/or uncontrolled medical conditions or other conditions that could affect their participation in the study.
- 3.2.15 Patients with any one of the following currently on or in the previous 6 months will be excluded: myocardial infarction, congenital long QT syndrome, torsade de pointes, left anterior hemiblock, unstable angina, coronary/peripheral artery bypass graft, or cerebrovascular accident.
- 3.2.16 Other uncontrolled intercurrent illness that would limit adherence to study requirements.

#### 3.3 Inclusion of Women and Minorities

Both men and women of all races and ethnic groups are eligible for this trial.

#### 4. REGISTRATION PROCEDURES

#### 4.1 General Guidelines for DF/HCC Institutions

Institutions will register eligible participants in the Clinical Trials Management System (CTMS) OnCore. Registrations must occur prior to the initiation of any protocol-specific therapy or intervention. Any participant not registered to the protocol before protocol-specific therapy or intervention begins will be considered ineligible and registration will be denied.

An investigator will confirm eligibility criteria and a member of the study team will complete the protocol-specific eligibility checklist.

Following registration, participants may begin protocol-specific therapy and/or intervention. Issues that would cause treatment delays should be discussed with the Principal Investigator (PI) of the registering site. If the subject does not receive protocol therapy following registration, the subject must be taken off study in the CTMS (OnCore) with an appropriate date and reason entered.

### 4.2 Registration Process for DF/HCC Institutions

Applicable DF/HCC policy (REGIST-101) must be followed.

### 4.3 General Guidelines for Other Investigative Sites

Eligible participants will be entered on study centrally at the Dana-Farber Cancer Institute by the Project Manager. All sites should call the Project Manager at [contact] to verify dose level availabilities.

Following registration, participants should begin protocol therapy within 5 days. Issues that would cause treatment delays should be discussed with the Sponsor-Investigator. If the subject does not receive protocol therapy following registration, the subject must be taken off study in the CTMS (OnCore) with an appropriate date and reason entered.

### 4.4 Registration Process for Other Investigative Sites

[figure not shown]
To register a participant, the following documents should be completed by participating site and e-mailed to the DFCI Project Manager.

- Copy of required assessments that support eligibility
- Signed informed consent document
- HIPAA authorization form (if applicable)
- Completed DFCI eligibility checklist

The participating site will e-mail the DFCI Project Manager to verify eligibility. The DFCI Project Manager will follow DF/HCC policy (REGIST-101) and register the participant on the protocol. The DFCI Project Manager will email the participant study number, and if applicable the dose treatment level, to the participating site. The DFCI Project Manager may also contact the participating site and verbally confirm registration.

